The primary outcome of this repeated measures RCT is the proportion of participants accurately identifying alcohol as a clear risk factor for breast cancer at 4-weeks post-randomisation. Inferences about the effect of the Health4Her intervention on the primary outcome will be based on a comparison, between treatment groups, of change from baseline to 4-weeks post-randomisation using a Cochran-Mantel-Haenszel test. This analysis tests for homogeneity of the odds ratio across strata (i.e. intervention and control). A binomial test (that is, a test of proportions) will be used as an ancillary analysis of the primary outcome (i.e. the difference in proportions between the two groups at 4-weeks post-randomisation).

Relevant covariates (from the list of potential covariates below) may also be used in further analysis, using generalised linear models (logistic regression) to make comparisons. Additional analyses may use covariates for post-stratification.

Secondary Outcomes

Alcohol Consumption

Alcohol consumption will be assessed by the Alcohol 14-day Timeline Follow-back (TLFB). Heavy drinking days are measured as >40 grams of alcohol (>4 Australian standard drinks). Alcohol consumption will also assessed by the AIHW alcohol frequency quantity items. Assessments are made at 0, 4 and 12 weeks and linear mixed models (continuous variables) or GLMMs or GAMMs (categorical / binary variables) will be used. The following outcomes will be analysed (transformed if necessary for analysis):

Secondary outcome 1 – Proportion of participants drinking less than or equal to 10 standard drinks per week at 4-weeks and 12-weeks post-randomisation. Derived from (operationalised in two ways):

- Has the participant consumed >10 standard drinks in week one AND/OR >10 standard drinks in week two? (tlfb_nhmrc_both_comprh)
- Has the participant consumed >10 standard drinks in both week one AND week two? (derived variable: tlfb_nhmrc_bothwks)

Secondary outcome 2 – Proportion of participants drinking less than or equal to 10 standard drinks per week at 4-weeks and 12-weeks post-randomisation, among only participants who drink more than 10 standard drinks per week at baseline.

Subgroup defined as either i. women who consumed >10 standard drinks in week one AND/OR >10 standard drinks in week two (tlfb_nhmrc_both_comprh) or ii. women who consumed >10 standard drinks in both week one AND week two (tlfb_nhmrc_bothwks).

Outcome derived from:

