 - derived from atttd_changerisk
 - Likert response

Potential covariates for exploratory analyses of primary and secondary outcomes

- age (continuous; categorical 40-49, 50-59, 60-69, 70+ years)
- lgbtq+
- education
- born in Australia
- culturally and linguistically diverse background
- household composition
- disability status
- alcohol consumption at baseline (drinking above/within current NHMRC guidelines, 14-day TLFB subscales scores, AIHW frequency quantity scores)
- QoL/health-related QoL at baseline (SF-12 mental and physical component scores, EUROHIS-QOL single item)
- health literacy at baseline (attitude and knowledge scores)

ⁱGraeme Tucker, Robert Adams, David Wilson. New Australian population scoring coefficients for the old version of the SF-36 and SF-12 health status questionnaires, Qual Life Res (2010) 19:1069-1076, DO 10.1007/s11136-010-9658-9

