## 14 STATISTICAL METHODS

### 14.1 Sample Size Estimation

Since the aims of this pilot RCT include preliminary hypothesis testing for effectiveness, a power and sample size calculation has been performed (Moore, Carter et al. 2011). Power and sample size estimates were carried out using PS: Power and Sample Size Calculation V3.1.2 (Dupont and Plummer 1990), assuming a type 1 error probability of  $\alpha < 0.05$ , 2-tailed, and equal-sized groups. Power calculations are based on the primary endpoint, proportion of participants who accurately identify alcohol as a clear risk factor for breast cancer.

Our sample size estimation is based on our previous online survey study with 391 women who have attended/are eligible to attend breast screening services (Health4Her Phase I). If the proportion of control participants who accurately identify alcohol as a clear risk factor for breast cancer is 0.22 and the true response rate for participants receiving the alcohol brief intervention is 12% greater at 0.34, and compensating for 20% attrition at follow-up, then 548 participants (274 per arm) will provide power of 80% to be able to reject the null hypothesis.

Given the lack of definitive evidence regarding alcohol BI effects in women, and particularly women of middle- and older-age in a breast screening setting, this powered pilot RCT will inform the development of a subsequent, comprehensive multicentre trial. This pilot RCT will generate preliminary data on intervention response using exploratory surrogate/proximal markers of effectiveness (e.g. proportion of participants accurately identifying alcohol as a breast cancer risk factor, proportion of participants drinking within guidelines, alcohol consumption and well-being), and will provide concrete estimates of risky alcohol consumption prevalence, and expected rates of missing data and participant attrition specific to the population under study (Moore, Carter et al. 2011).

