### 14.2 Statistical Analysis Plan

A detailed statistical analysis plan will describe the statistical methods for each outcome as well as how missing data will be dealt with. Data will be collated, cleaned and validated, using programmed edit checks, in a database that will be locked prior to analyses. All statistical tests will be two-tailed, with alpha level set to 0.05. Statistical analyses will be adjusted for multiple comparisons when indicated. 95% confidence intervals will be reported throughout. All randomised participants will be included in the analysis (i.e. intention-to-treat) for primary and secondary outcomes. Demographic characteristics (e.g. age) and baseline measurements (e.g. knowledge of alcohol as a clear risk factor for breast cancer, alcohol consumption) will be summarised and reported by intervention arm. The analyses will examine change in outcomes over time (4-weeks and/or 12-weeks) relative to baseline. The complete details of the analyses will be specified in a Statistical Analysis Plan that will be reviewed and approved by a study team prior to database lock. Analyses will be conducted using the most appropriate procedures in R and STATA.

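### Primary inference on the 4-week answer is not adjusted for the woman's own baseline answer to the same item; adjustment is only optional and exploratory

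*SAP*

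**What the plan says.** The hypothesis (Protocol 3.1) and the sample size (Protocol 14.1) both concern the difference between arms in the proportion who call alcohol a clear risk factor at 4 weeks. Protocol 14.1 takes 0.22 for the control arm, 0.34 for the active arm and a 20% loss to follow-up. Its conclusion reads: "then 548 participants (274 per arm) will provide power of 80% to be able to reject the null hypothesis". Protocol 14.2 adds: "All statistical tests will be two-tailed, with alpha level set to 0.05".

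The SAP, under Primary Outcome, commits to two analyses:

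- Inference rests on a between-arm comparison of change from baseline to 4 weeks by a CMH test. This is described as a test of whether the odds ratio is the same across strata, the strata being the two arms.
- "A binomial test (that is, a test of proportions) will be used as an ancillary analysis of the primary outcome", namely the difference between arms at 4 weeks.

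Adjustment comes next, as an option: "Relevant covariates (from the list of potential covariates below) may also be used in further analysis". The list it points to is headed as potential covariates for exploratory analyses, and one entry is "health literacy at baseline (attitude and knowledge scores"). Post-stratification by covariates is optional too. The SAP's general section on outcomes with two or fewer time points mentions logistic regression with subject random effects, but only if covariates are required.

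The same item is planned for every woman before randomisation (Protocol 6, 8.2 and 14.2).

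**The concern.** The baseline answer to the same question is probably the best available predictor of the 4-week answer. A trial that collects it can use it in three ways:

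- leave it out, as the binomial test does;
- subtract it in full, as a change comparison does;
- adjust for it by the amount that the data support.

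The third is the most precise of these in large samples, and it is the only one to which the SAP does not commit.

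Two things are at stake. The first is the width of the interval for the primary effect, and with it the power. The second is chance imbalance at baseline: an unadjusted comparison lets part of it through, and subtracting the whole baseline answer over-corrects for it. Leaving adjustment optional also leaves open, until the data are in hand, whether it is done and with which covariates.

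**Working it through.** **Inputs from the documents.** Control 0.22, active 0.34 and 20% attrition (Protocol 14.1); 274 per arm (Protocol 5.1 and 14.1); two-sided 0.05 (Protocol 14.2); 1:1 allocation (Protocol 6).

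**Assumptions.** Baseline proportion 0.22 in both arms. The correlation ρ between the baseline and 4-week answers in the control arm is not given, so 0.3, 0.4 and 0.5 are shown.

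**The plan's own figure.** Pooled two-proportion formula, mean proportion 0.28:

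n = [1.96 √(2 × 0.28 × 0.72) + 0.8416 √(0.22 × 0.78 + 0.34 × 0.66)]² / 0.12² = (1.2445 + 0.5296)² / 0.0144 = 218.6, so 219 per arm.

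219 / 0.8 = 273.75, so 274 per arm and 548 in all. The stated figure reproduces. Power at 219 per arm is 80.1% with the pooled variance and 80.6% with the unpooled variance used below.

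**Variances.** vB = vC = 0.22 × 0.78 = 0.1716; vA = 0.34 × 0.66 = 0.2244. Let cC and cA be the baseline-to-week-4 covariances in the two arms. The variance of the estimated difference in proportions is then:

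- unadjusted: (vC + vA) / n
- paired change: (2vB + vC + vA − 2cC − 2cA) / n
- baseline-adjusted: (vC + vA − (cC + cA)² / (2vB)) / n

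Power = Φ(0.12 / SE − 1.96).

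**Unadjusted.** SE = √(0.3960 / 219) = 0.0425, ratio 2.82, power 80.6% whatever the correlation.

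**Worked case, ρ = 0.4.** cC = 0.4 × 0.1716 = 0.0686. With the same underlying (latent-normal) association in the active arm, cA = 0.0785, so cC + cA = 0.1471.

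- Paired change: (0.3432 + 0.3960 − 0.2942) / 219, SE 0.0451, power 75.9%.
- Adjusted: (0.3960 − 0.1471² / 0.3432) / 219 = 0.3330 / 219, SE 0.0390, power 86.8%.

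**A less favourable model.** Suppose that the whole 12-point gain comes from women who did not know at baseline. The share correct at both visits is then the same in both arms: 0.22² + 0.0686 = 0.1170. So cA = 0.1170 − 0.22 × 0.34 = 0.0422, an active-arm correlation of about 0.22. Paired change has SE 0.0486 and power 69.5%; adjusted has SE 0.0406 and power 84.1%.

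| Control-arm ρ | Unadjusted | Paired change | Adjusted | Paired change, non-knowers only | Adjusted, non-knowers only |
|---|---|---|---|---|---|
| 0.3 | 80.6% | 69.5% | 84.1% | 64.0% | 82.2% |
| 0.4 | 80.6% | 75.9% | 86.8% | 69.5% | 84.1% |
| 0.5 | 80.6% | 82.7% | 90.1% | 75.5% | 86.7% |

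**Simulation.** With 40,000 simulated trials per setting and the same correlation in both arms, power at 0.3, 0.4 and 0.5 was 69.5%, 75.9% and 83.3% for paired change. Linear adjustment gave 83.6%, 86.4% and 90.1%. A CMH test stratified by the baseline answer gave 83.5%, 86.2% and 89.9%. Under no effect, checked at 0.3 and 0.5, all three rejected in 4.8% to 5.1% of trials.

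**Chance imbalance.** The standard error of the baseline difference between arms is √(2 × 0.1716 / 219) = 0.040, or 4 points against a 12-point target effect.

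**The case against.** The strongest reply is that nothing planned has been lost. The trial was sized for an unadjusted comparison at 80%, and 548 delivers it. With the 558 women that the SAP reports as randomised and 20% attrition, power is about 80.8%. The main analysis does use baseline, through change, and Protocol 14.2 says that analyses look at change from baseline. Covariate adjustment is also permitted already. On this view the point is one of efficiency, not validity. Most of that stands.

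Three stronger readings are tempting, and the documents do not support them.

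- *The trial gives up about 10 points of power.* That gap is adjusted against the ancillary binomial test at a correlation of 0.5. The correlation has no source in the documents, and the binomial test is not the basis for inference. At 0.3 the gain over that test is about 3.5 points. If only non-knowers respond, the gain is about 6 points at 0.5 and under 2 at 0.3.
- *The committed analyses ignore baseline.* Only the binomial test does.
- *The baseline answer is always available.* It is planned for everyone, but Protocol 6 and 12.1 allow part of the baseline assessment to be self-completed on paper, so some items may be missing.

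What the reply does not answer is the comparison with the test that decides the trial. Where adjustment gains little over the binomial test, it gains most over change: 84.1% against 69.5% at a correlation of 0.3. The power figures for change also assume a correctly paired comparison, which the SAP's description of the CMH test does not make clear.

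**Conclusion.** The point holds as one of forgone precision, and the improvement costs almost nothing. No committed analysis of the primary outcome uses the baseline answer as a covariate or stratifier.

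At control-arm correlations of 0.3 to 0.5, adjustment adds about 3.5 to 9.5 points over the unadjusted test (about 1.6 to 6 if only non-knowers respond). Over a correctly paired change comparison it adds about 15 down to 7 points (about 18 down to 11 if only non-knowers respond). Adjusted power is above both committed analyses in every row of the table.

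The unadjusted test keeps its planned 80%. The change comparison does not, below a correlation of roughly 0.5: it crosses 80% at about 0.46 under the first model and about 0.57 under the second. So the analysis named for inference may have less power than the sample size section states.

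All of this rests on the plan's 0.22, 0.34 and 20%, an assumed baseline proportion of 0.22, and correlations that the documents do not give.

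**What to change.** In the SAP under Primary Outcome, replace the sentence that rests inference on the CMH change test. Primary inference should come from logistic regression of the 4-week answer (clear risk factor, yes or no) on arm and the baseline answer to the same item. Report it as a standardised (marginal) difference in proportions with a robust 95% confidence interval, which keeps the quantity used for the sample size in Protocol 14.1. If only a test is wanted, a CMH test of arm by 4-week answer, stratified by the baseline answer, does practically the same job.

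Keep the unadjusted binomial test and any change comparison, and label both as sensitivity analyses so that the order is clear. Give a missing baseline item its own category. Use the same model for the three knowledge items of secondary outcome 6, which follow the same CMH plan.

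The cost is SAP wording and one regression per item on data already planned for collection, with no new participants or visits. The change should be made before database lock; if lock has passed, the adjusted analysis should be reported as a later decision.

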In general, outcome variables with repeated measurements will be analysed by fitting linear mixed models (for continuous outcomes or outcomes treated as continuous, such as 5-point Likert scales) or (for categorical / binary outcomes) generalised linear mixed models (GLMMs) or generalised additive mixed models (GAMMs), with fixed effects for treatment and time, and their interaction, and random effects for subjects and assessments within subjects, using restricted maximum likelihood (REML) or similar algorithms. These models allow missing values to be accommodated.

These methods will allow the most suitable variance-covariance model for the repeated measures to be selected, using Akaike's Information Criterion, and, if appropriate, commonality of nonlinear trends over time to be explored via splines. The F-test (or equivalent chi square test, t-test of coefficients in logistic regression) will be used to test for an overall group by time interaction in outcomes measured at all three follow-up times (0, 4 and 12 weeks).

Outcomes measured at two or fewer time points

For outcome variables measured at two or fewer time-points, different models will be used, depending on the nature of the outcome variable:

- Where the outcome is binary and proportions are required, a test of change in proportions for categorical outcomes, e.g. the Cochran-Mantel-Haenszel test, will be applied or, if covariates are required in the analysis, logistic regression with random effects for subjects. Such logistic regression models are instances of GLMMs or GAMMs.
- 2. For continuous outcomes or outcomes treated as continuous (such as 5-point Likert scales) linear mixed models will be used (as for outcomes measured at three time-points).
- 3. In simple cases of the preceding points, the analysis may reduce to (in the sense of being equivalent to) a test of whether there is a difference between the two groups (treatment and control) in the changes in the mean (for continuous outcomes). If just one time point is involved, we may use a binomial test of proportions (for categorical outcomes).

Outcomes measured at 4 and 12 weeks but without a baseline measurement will be covered by this case.

Missing values

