Where possible, missing values will be handled under the missing at random assumption; that is, unless there is good reason to believe this assumption is untenable. In cases of doubt the analysis will be re-done with (a) missing values imputed and (b) the corresponding subjects removed from the analysis.

Outcomes where there is no baseline measure possible (that is, by design) will not be treated as having the baseline value missing, but rather as belonging to the two time-point case.

Exploratory analyses

Exploratory analyses will be performed using the same methods as for the primary and secondary outcomes (as appropriate) plus, optionally, such other modelling strategies as may be useful (e.g. random forests or decision trees as exploratory tools, or other classification tools).

In exploratory analyses of outcomes measured at three time-points, mixed models with covariates as relevant (see list of potential covariates below), including their interactions with treatment group, will be fitted in order to identify moderating factors. Categorical, ordinal and binary outcomes will be analysed in a similar way using generalised linear mixed models (GLMMs) or generalised additive mixed models (GAMMs).

In exploratory analyses of outcomes measured at two time-points, logistic regression with random effects for subjects will be utilised to assess the effects of potential covariates (see list of potential covariates below).

Statistical software

Analyses will be conducted using the most appropriate procedures in GenStat, R, SAS or STATA and additional analyses not specified in the published protocol or this addendum will be regarded as exploratory.

Statistical Analysis of the Primary and Key Secondary Outcome Variables

Primary Outcome

The primary analysis will take place after all subjects, not known to have withdrawn or not deemed lost to follow-up, have had their 12-week assessments, based on the intention to treat (ITT) principle (i.e. subjects' data are analysed as randomised and as stratified).

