- Has the participant consumed >10 standard drinks in week one AND/OR >10 standard drinks in week two? (tlfb_nhmrc_both_comprh)
- Has the participant consumed >10 standard drinks in both week one AND week two? (tlfb_nhmrc_bothwks)

Secondary outcome 3 – Change in alcohol consumption at 4-weeks and 12-weeks post-randomisation. Derived from:

- TLFB: Drinking Days (tlfb_drinkdays)
- TLFB: Drinking Days with > 2 Standard Drinks (tlfb_days_2stand)
- TLFB: Drinking Days with > 4 Standard Drinks (tlfb_days_4stand)
- TLFB: Total Standard Drinks in the Past 14 days (tlfb_totalmonth)
- Derived from AIHW frequency quantity items: average standard drinks per day (derived variable: alc_perday)
- AIHW frequency: In the past month, how often did you have an alcoholic drink of any kind? (alc_freq)
- AIHW quantity: quantity of alcohol consumed on a typical day calculated in standard drinks (alc_quant_sd)

Secondary outcome 4 – Change in alcohol consumption at 4-weeks and 12-weeks postrandomisation, among only participants who drink more than 10 standard drinks per week at baseline

Subgroup defined as either i. women who consumed >10 standard drinks in week one AND/OR >10 standard drinks in week two (tlfb_nhmrc_both_comprh) or ii. women who consumed >10 standard drinks in both week one AND week two (tlfb_nhmrc_bothwks).

Outcome derived from:

- TLFB: Drinking Days (tlfb_drinkdays)
- TLFB: Drinking Days with > 2 Standard Drinks (tlfb_days_2stand)
- TLFB: Drinking Days with > 4 Standard Drinks (tlfb_days_4stand)
- TLFB: Total Standard Drinks in the Past 14 days (tlfb_totalmonth)
- Derived from AIHW frequency quantity items: average standard drinks per day (alc_perday)
- AIHW frequency: In the past month, how often did you have an alcoholic drink of any kind? (alc_freq)
- AIHW quantity: quantity of alcohol consumed on a typical day calculated in standard drinks (alc_quant_sd)

Alcohol health literacy

Secondary outcome 5 – Change in participants' attitudes regarding alcohol and breast cancer risk from baseline to 4-weeks post-randomisation. A linear mixed model (for repeated measures) will be used to analyse the Likert scale response (derived from atttd_alcrisk). Transformations of response variables will be used as appropriate, such as in GLMMs or GAMMs.

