**At 4-weeks and 12-weeks post-randomisation:**

- *Proportion of participants drinking less than or equal to 10 standard drinks per week (i.e. within current Australian Alcohol Guidelines) (14-day Timeline Followback; TLFB)*
- *Among participants who drink more than 10 standard drinks per week at baseline: Proportion of participants drinking less than or equal to 10 standard drinks per week (14-day TLFB)*
- *Change in alcohol consumption (14-day TLFB; AIHW alcohol frequency/quantity items)*
- *Among participants who drink more than 10 standard drinks per week at baseline: Change in alcohol consumption (14-day TLFB; AIHW alcohol frequency/quantity items)*
- *Change in general health (SF-12)*
- *Change in quality of life (EUROHIS-QOL single item)*

We hypothesise that compared to those in the control group, at 4-weeks and 12-weeks post-randomisation:

- (iv) A significantly greater proportion of participants receiving alcohol brief intervention will be drinking less than or equal to 10 standard drinks per week (i.e. within current Australian Alcohol Guidelines)

- 
- (v) Of participants who drink more than 10 standard drinks per week, a significantly greater proportion of those receiving alcohol brief intervention will be drinking less than 10 standard drinks per week
  - (vi) Participants receiving alcohol brief intervention will report significantly greater reductions in alcohol consumption
  - (vii) Of participants who drink more than 10 standard drinks per week, those receiving the alcohol brief intervention will report significantly greater reductions in alcohol consumption
  - (viii) Participants receiving alcohol brief intervention will report significantly greater improvements in general health and quality of life

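### Secondary outcome 2: the named group-by-time interaction test cannot test hypothesis (v), because with matched definitions baseline is 0% in both arms

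*SAP*

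**What the plan says.** Under Secondary Outcomes, Alcohol Consumption, the SAP sets the framework for all the alcohol outcomes: "Assessments are made at 0, 4 and 12 weeks and linear mixed models (continuous variables) or GLMMs or GAMMs (categorical / binary variables". Secondary outcome 2 falls under that sentence and is reported "at 4-weeks and 12-weeks post-randomisation, among only participants who drink more than 10 standard drinks per week at baseline". It has no test of its own, whereas secondary outcomes 6 and 7 do.

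The section on outcomes with more than two time points supplies the test. An F-test, chi-square test or t-test of logistic coefficients is used to "test for an overall group by time interaction in outcomes measured at all three follow-up times (0, 4 and 12 weeks".

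Two TLFB variables define the baseline subgroup: "Subgroup defined as either i. women who consumed >10 standard drinks in week one AND/OR >10 standard drinks in week two" (definition i), or above 10 in both weeks (definition ii). The outcome is derived from the same two variables; the second reads "Has the participant consumed >10 standard drinks in both week one AND week two? (tlfb_nhmrc_bothwks". The SAP does not say which subgroup definition goes with which outcome definition.

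Hypothesis (v) in protocol section 3.2 compares the arms at 4 and 12 weeks: "Of participants who drink more than 10 standard drinks per week, a significantly greater proportion of those receiving alcohol brief intervention" will be under the limit. Protocol section 14.2 speaks of change relative to baseline.

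Two further SAP rules matter. Under Missing values: "Outcomes where there is no baseline measure possible (that is, by design) will not be treated as having the baseline value missing"; such outcomes go to the two-time-point case. Under Statistical software: "additional analyses not specified in the published protocol or this addendum will be regarded as exploratory".

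**The concern.** Selecting women because they exceed the limit at baseline, and then including that same status as the first of three repeated measurements, makes the baseline row constant. It carries no information on treatment, yet the interaction test takes it as the reference.

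Hypothesis (v) asks whether more of these women in the active arm are within the limit at follow-up. A benefit that is present at week 4 and fully kept at week 12 is the result the trial would most like to find, and it is the one the named test cannot see. A null interaction could then be reported as no benefit. The informative comparison is not named as the test, so its status as a confirmatory analysis would be open to dispute.

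**Working it through.** The documents give no subgroup size, response rate or power for secondary outcome 2, so there is no planned figure to reproduce. The 548 in protocol section 14.1 concerns the primary outcome only. The significance level, 0.05 two-tailed, is from protocol section 14.2.

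**1. Baseline status by pairing.** A woman counts as within the limit if the answer to the outcome variable is no.

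| Subgroup | Outcome | Within limit at baseline |
|---|---|---|
| i (either week above 10) | i | 0% by construction |
| ii (both weeks above 10) | ii | 0% by construction |
| ii | i | 0% by construction |
| i | ii | can exceed 0% |

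In the last row, a woman with 12 drinks and then 5 enters the subgroup but already counts as within the limit.

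**2. What the interaction tests.** Let A be arm, and T4 and T12 the visit indicators:

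logit P = a + b·A + c4·T4 + c12·T12 + d4·A·T4 + d12·A·T12

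The log odds ratios between arms are b at baseline, b + d4 at week 4 and b + d12 at week 12. The null hypothesis is d4 = d12 = 0. With 0/n in both baseline cells, a goes to minus infinity, and the baseline rows fit perfectly for any finite b. So b can take whatever value the follow-up data want. The null reduces to one constraint: equal odds ratios at weeks 4 and 12.

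**3. Numerical example** (assumed 60 per arm, 0/60 in both baseline cells; the likelihood ratio (LR) statistics ignore within-woman correlation).

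- 18/60 v 30/60 at both visits: odds ratio (30/30)/(18/42) = 2.33. Interaction LR = 0.00, p = 1.0. Group effect LR = 10.1, p = 0.0015.
- 18/60 v 48/60 at both visits: odds ratio (48/12)/(18/42) = 9.33. Interaction LR = 0.00. Group effect LR = 63.6.

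The fitted interaction coefficients were ln 2.33 = 0.85 and ln 9.33 = 2.23, with standard errors of about 291,000. Such values depend on when the fit stops, which is the mark of separation, so the coefficient t-test is unusable.

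**4. Rejection rate under a constant odds ratio.** The statistic follows a chi-square with 1 df but is referred to 2 df, where the 5% critical value is 5.99. P(chi-square with 1 df > 5.99) = 0.0144, or 1.4%. This large-sample result needs no assumption on subgroup size or rates, but the within-woman correlation must be modelled.

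**5. Simulation** (assumed 30, 60 or 100 per arm; control 30% within the limit; latent correlation between visits 0 or 0.5; 6000 trials per scenario; ordinary logit without subject effects). The comparator is a z test on each woman's mean over weeks 4 and 12.

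| Active arm, week 4 / week 12 | Interaction rejects | Averaged arm comparison rejects |
|---|---|---|
| 30 / 30 (no effect) | 0.3% to 2.1% | – |
| 42, 55 or 70, same at both visits | 0.2% to 1.9% | 23% to 71% for 42; 69% to 100% for 55 |
| 55 / 42 | 2% to 11% | – |
| 55 / 30 | 10% to 51% | – |

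**6. Random-intercept logit, closer to the SAP's model.** In the step 5 scenarios with a constant effect, at 60 per arm and 1000 trials each, the interaction rejected 0.9% to 1.2%. In a separate simulation (random-intercept SD 1.5; about 0.36 v 0.57 within the limit at both visits; 300 trials per scenario), it rejected 2%, 1% and 1% at 30, 60 and 100 per arm. The arm effect at follow-up rejected 54%, 84% and 97%. In every data set checked, the three-time interaction LR matched the one from weeks 4 and 12 alone to within 0.001.

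**The case against.** The strongest reply is that this is the strictest reading of the SAP. The general section opens with a qualifier, the alcohol block names model families rather than a test, and outcome 2 is worded as proportions at 4 and 12 weeks, not as change. The arm contrasts at those visits come from the SAP's own model and address a hypothesis the protocol states, so calling them exploratory may go too far. An analyst might also treat a baseline fixed by selection as no baseline and use the two-time-point case. Separation would probably be noticed when the model was run.

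Some of this stands. The contrasts can be estimated, and their exploratory status is arguable. But the protocol states a hypothesis, not an analysis, and no other test is named for this outcome. The two-time-point rule covers outcomes with no baseline measurement; here one is taken.

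Other limits also stand. Complete blindness holds only when the odds ratio is equal at both visits. It depends on the logit link: on a linear probability scale the 2-df interaction rejected 48%, 76% and 93% of the time at 30, 60 and 100 per arm in the separate random-intercept simulation. The SAP, however, specifies generalised mixed models and logistic coefficients for binary outcomes. The mismatched pair (subgroup i, outcome ii) escapes the structural zero, although parallel lists read most naturally as matched. The lowest simulated rates in step 5 come from leaving out the subject effect. Finally, this is one of nine secondary outcomes in a self-described pilot, and outcome 4 examines change in consumption in the same women without this problem.

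**Conclusion.** The concern holds. With matched definitions, or with subgroup ii and outcome i, the test named for secondary outcome 2 asks whether the effect changes between weeks 4 and 12. It does not ask whether there is an effect. Under a constant odds ratio it rejects in about 1.4% of large-sample trials whatever the benefit, the same as under no effect. That figure rests on the logit scale and on correlation being modelled. All other powers rest on assumed subgroup sizes and rates, and an effect that fades is partly detectable. This should be fixed, but it affects one secondary outcome only and leaves the primary outcome and sample size untouched.

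**What to change.** For secondary outcome 2, exclude the baseline row and model only the 4- and 12-week responses, using a GLMM or GEE with arm, time and arm by time. Name the test of hypothesis (v): the arm effect at 4 weeks, at 12 weeks, or jointly. Adjustment for baseline TLFB total drinks is optional. State that subgroup and outcome definitions are matched, i with i and ii with ii.

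The cost is one or two sentences in the SAP and a small change to the code. No new data are needed.
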